9.3 Study Day and Time from Randomization

Study Day 1 is defined to be the day of the randomization visit (visit 1, week 0). Time from randomization (in days) for subsequent visits is defined to be visit date – date of randomization visit +1.

9.4 Visit Windows

Following randomization, the visits are scheduled every 4-8 weeks, but the actual times of the visits may deviate from the scheduled times. With spirometry data, consideration needs to be taken to remove the rejected spirometry assessments for analysis before applying the visit windowing.

To allow for any presentation that summarizes values by visit, visit windows will be defined according to the table below. Measurements (both scheduled and unscheduled) will be allocated to visits (and analyzed) as reported in **Table 1**.

Table 1: Visit windows.

Nominal Visit	V1	V2	V3	V4	V5	V6	V7	V8	V9/EoT	V10/EoS
Nominal Week	W0	W4	W8	W12	W16	W24	W32	W40	W48	W52
Nominal Day	1	29	57	85	113	169	225	281	337	365
Time (days) from Randomization***	0	1-42	43-70	71-98	99-140	141-196	197-252	253-308	*309-364 **309-385	*365-385

*Patients who do not consent or participate in BT – L-CsA – 303 – FU (BOSTON-3).

**Patients who consented and participated in BT – L-CsA – 303 – FU (BOSTON-3), and will not have a V10 / EoS.

*** Visit windows are based on [visit date – date of randomization visit] formula for time (days) from randomization.

Data collected after 385 days or 364 days (as applicable, as per the table above) will not be used for analyses but will be included in the listings. If there are two or more measurements assigned to a nominal visit, only the one closest to the scheduled time of the visit will be used in the analysis, unless an additional measurement will be the last measurement during a patient's trial participation (e. g., in case of an unscheduled visit before premature withdrawal), which will always be included into the analysis.

In the case a scheduled visit is performed in the same date of an unscheduled visit, the scheduled visit assessments will be used; in the specific case of spirometries, if the spirometry data is accepted in the scheduled visit, the scheduled visit data will be used, otherwise (if the spirometry in the scheduled visit is rejected) if the spirometry data is accepted in the unscheduled visit, the unscheduled visit data will be used.

Finally, if a nominal visit has more than one accepted spirometry data assigned, and some of them are performed after IMP inhalation, then only the spirometries done before inhaling the IMP will be used for the visit window mapping rules described above. Instead, if all the accepted spirometries of the nominal visit are done after inhaling the IMP, then all of them will be considered for the above mapping rules. Spirometries collected at 1h and 4h post dose will be used only for safety evaluations and will only be presented in data listings.

Windowing will be applied to the data prior to any missing data imputation.

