14.1.2 Working Hypothesis

The alternative hypothesis (H_1) for this trial is that L-CsA plus SoC is superior to SoC alone in preserving FEV₁, i.e., under H_1 it is expected that patients treated with L-CsA plus SoC will exhibit a smaller mean FEV₁ decline between baseline and the end of Week 48 than those who receive SoC alone.

Due to the decrease in sample size (see section 8.2) then there will be an underpower to assess the statistical hypothesis, and instead the primary analysis will be descriptive in nature.

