14.1.5 Specification of the Covariance Model

The model for the mean uses the actual times of the visits as a continuous variable instead of the scheduled visit times. Therefore, the covariance model will also use the actual visit times, using random effects. For valid inference, the model for the covariance should be correctly specified.

Thus, the preference will be for models with relatively many parameters in order to ensure robust estimation of the covariance, though this may lead to a loss of efficiency.

Therefore a model will be specified with four per patient random effects: intercept, t , t^2 , t^3 , with an unstructured covariance matrix. This covariance model contains 11 parameters, ensuring sufficient robustness. In case the model does not converge, or the covariance matrix is not positive definite, we will drop terms from the highest order random effect.

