14.2.2 T-test

The mean treatment difference in change from baseline up to Week 48 in FEV_1 , standard deviation and 95% confidence interval will be presented. A two-sample t-test will be performed by treatment group at each visit using change from baseline in FEV_1 .

In case of death or re-transplantation events, FEV_1 will be imputed as zero at each nominal day post event.

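### For patients outside BOSTON-3, the Week-48 window in SAP Table 1 also takes in Week-52 follow-up visits held on time or early

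*SAP*

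**What the plan says.** SAP 9.4 allocates every measurement, scheduled or not, to an analysis visit by day. Table 1 gives V9 as "309-364 309-385". Patients outside BOSTON-3 have V9 on days 309–364 and V10 on days 365–385. Patients in BOSTON-3 have no V10, and their V9 window runs to day 385.

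Footnote *** sets the day count as visit date minus randomization date, the "formula for time (days) from randomization". SAP 9.3 defines the same quantity differently: "Time from randomization (in days) for subsequent visits is defined to be visit date" minus the randomization date, plus 1.

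When several measurements share a window, the one closest to schedule is used. The exception is a patient's last measurement, "which will always be included into the analysis". Section 9.4 also states: "Data collected after 385 days or 364 days (as applicable, as per the table above) will not be used for analyses".

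The protocol's Schedule of Activities puts V9 at Week 48 ± 14 days and V10 at Week 52 ± 7 days. SAP 7.1 describes V10 as a safety follow-up four weeks after V9, for patients not rolling over and, if possible, those who withdrew consent.

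**The concern.** The eCRF label does not protect a V10 value, because the window decides the analysis visit. If V10 falls inside the V9 window, a value from about Week 51–52 is treated as Week 48.

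The analyses exposed are those that use visit labels: the by-visit summaries, the Week-48 ANCOVA (SAP 14.2.1), the subgroup t-tests (SAP 14.5) and SAP 14.2.2, where "A two-sample t-test will be performed by treatment group at each visit". These tests assume one record per patient. The laboratory and vital-sign tables by visit use the same windows.

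The fault is one of timing. The SAP deliberately keeps FEV1 measured after L-CsA has stopped, so being off drug does not by itself disqualify a value.

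**Working it through.** **Inputs.** Windows and day count: SAP 9.4, Table 1 and footnote ***. Competing count: SAP 9.3. Visit tolerances: protocol section 14, Schedule of Activities. Number randomized (62): SAP 8.2.

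**Reproducing Table 1.** The nominal days equal 7 × week + 1: 29, 57, 85, 113, 169, 225, 281, 337, 365. All match. The window row is on the elapsed count, 7 × week: 28, 56, 84, 112, 168, 224, 280, 336, 364. Midpoints of neighbouring elapsed days are 42, 70, 98, 140, 196, 252, 308 and (336 + 364)/2 = 350. The first seven equal the printed upper limits of V2 to V8. Only the V9/V10 limit departs: 364 is printed where the midpoint is 350. On its own count, the V10 window opens one day after Week 52 and has no early tolerance.

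**Where an in-tolerance V10 lands under Table 1**

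| V10 timing and day count | Possible days | Labelled V9 (≤364) | Labelled V10 (≥365) |
|---|---|---|---|
| Week 52 ± 7, footnote *** (364 ± 7) | 357–371 | 8 of 15 | 7 of 15 |
| Week 52 ± 7, +1 count (365 ± 7) | 358–372 | 7 of 15 | 8 of 15 |
| V9 + 28, footnote *** (336 ± 14, + 28) | 350–378 | 15 of 29 | 14 of 29 |
| V9 + 28, +1 count | 351–379 | 14 of 29 | 15 of 29 |

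An on-time V10 is mislabelled on the footnote *** count (day 364) but not on the +1 count (day 365). An early V10 within tolerance is mislabelled on both.

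**Does the tie rule remove it?** An in-tolerance V9 lies at most 14 days from day 336. A V10 on days 357–364 lies 21–28 days away, so closest-to-schedule keeps V9. Two routes remain. First, if the V9 spirometry is missing or rejected, V10 is the only Week-48 record; SAP 9.4 removes rejected sessions before windowing. Second, V10 is normally the last measurement, and the last measurement is always included, which gives two Week-48 records.

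**The cutoff sentence.** Neither group in Table 1 has 364 as its last usable day; both run to 385. If 364 were applied to patients outside BOSTON-3, a V10 on day 365 would be dropped while one on day 364 counted as Week 48.

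**Weight of one patient.** 62/2 = 31 per arm, assuming an even split; 1/31 = 3.2%.

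**Check of a 350/351 boundary (footnote *** count).** Allowed V9 days 322–350: 29 of 29 stay V9. Allowed V10 days 357–371: 15 of 15 map to V10. With V10 = V9 + 28, 28 of 29 map to V10; the exception is day 350, after a V9 on day 322. If the +1 count were kept with these limits, a V9 on day 351 would be lost (28 of 29), so the day count has to be settled first.

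**The case against.** The strongest reply is that harm needs unusual circumstances. With a valid V9, the closest-visit rule keeps it. The last-measurement exception is illustrated by an unscheduled visit before withdrawal, and a scheduled V10 is not plainly an additional measurement. SAP 14.1.1 and 14.1.3 tie the endpoint to visit 9 and the model to visits 2 through 9. The V10 spirometer is redacted in footnote 5 of the Schedule of Activities; if it is the home device, the primary on-site FEV1 analyses are untouched. Day counts such as 8 of 15 are not patient counts. The model is also robust here: "The model for the mean uses the actual times of the visits as a continuous variable". And "instead the primary analysis will be descriptive in nature".

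Much of this limits the size of the problem, and it stands. It does not remove the fault. Visit 9 is itself assigned by the window, so naming visit 9 does not exclude a V10. The exception's example is only an example, and its wording is general. The closest-visit rule does nothing when V9 is missing or rejected. Reading 364 as a cutoff for patients outside BOSTON-3 would indeed empty their V10 column, so that reading is unlikely; the sentence still does not say to whom 364 applies.

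A further objection is that one sentence keeping V10 out of V9 would be enough without moving the limits. It would not cover a V9 that was never held, and it would leave V10 values on days 357–364 without any window.

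**Conclusion.** The point holds. As written, Table 1 labels V10 visits held on time or early as Week 48 on the footnote *** count, and early ones on either count: 8 or 7 of the 15 allowed days. No readable text prevents such a value from being the sole Week-48 record, or a second one.

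The consequence is moderate. Only patients outside BOSTON-3 with a V10 are exposed. Their number is not stated, and neither the size nor the direction of any FEV1 bias can be computed from the documents. In the mixed model such a value would enter at about day 357–364 and affect only the tail of the fitted curve. Whether on-site or home spirometry is affected depends on redacted text, and all analyses are declared descriptive. It should be fixed because the arms are small and the correction is cheap.

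**What to change.** 1. For patients with a V10, set V9 to days 309–350 and V10 to days 351–385 on the footnote *** count. State the V9 window for patients outside BOSTON-3 who have no V10; it can stay as it is.
2. Use one day count in SAP 9.3 and 9.4, and say to whom the 364-day and 385-day limits apply.
3. State that a V10 follow-up held after a completed Week-48 V9 is never mapped to V9 and is not covered by the last-measurement exception. This also settles the day-350 case.
4. Use one record per patient per visit in the ANCOVA and t-tests. End-of-treatment visits at early withdrawal, which are also recorded as Visit 9, stay allocated by day as now.

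The cost is two table cells and three or four sentences; no new data are needed. There is one trade-off: in a patient with a V10, a late V9 on days 351–364, already outside its ± 14 days, would no longer count as Week 48.

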#### 14.2.7 Unscheduled Visits

Whenever medically warranted, the Investigator may ask the patient to appear or the patient may elect to appear at the clinic for an unscheduled visit. All medical measures performed as appropriate shall be documented in the Case Report Form for unscheduled visits.

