8.2 Sample Size Considerations

The initial sample size was based on the following considerations. Assuming a treatment group difference for mean FEV₁ change from baseline of 200 mL (0.2 L) and a standard deviation of 350 mL (0.35 L) at the end of treatment Week 48, an independent samples t-test with a one-sided type I error level of $\alpha=0.025$ will have at least 80% power to reject the null hypothesis when the sample size in each treatment group is at least 50 patients. To compensate for a loss of power due to premature withdrawals, a total of 110 patients were initially planned to be randomized.

In accordance with the amended version of the protocol (version 5.0) and following Food and Drug Administration **CCI** [REDACTED]

[REDACTED]
[REDACTED]
[REDACTED]
[REDACTED].

It was anticipated that approximately 160-170 patients have been randomized in BOSTON-2 and approximately 60 patients in BOSTON-1. 169 patients were actually randomized in BOSTON-2 and 62 patients in BOSTON-1.

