14.1.3 Analysis Model

The primary efficacy analysis will be carried out using a LMM for repeated measurements, using all observed available FEV₁ measurements. In case of death or re-transplantation events, FEV₁ will be imputed as zero at each nominal day post event.

The dependent variables are the absolute change from baseline of FEV₁ measurements at visit 2 (i.e., the first post-baseline visit) through visit 9 (Week 48). For the definition of baseline FEV₁ please refer to section 8.1.1.

A flexible and robust model will be chosen for the random part of the LMM according to a pre-specified stepwise procedure (see next section). The original protocol considered the fixed part of the LMM containing the following (except from the intercept): time cubic splines, treatment, the interactions of time splines by treatment, baseline FEV₁, the interactions of time splines with the baseline FEV₁, region (North America versus all other countries together), underlying indication for lung transplant (COPD versus all others), and use of azithromycin at randomization (i.e. Baseline, Visit 1). Due to the reduced sample size (see section 8.2), the covariates will be selected taking into account model convergence (as detailed below).

The primary efficacy parameter will be estimated from the model by the adjusted difference between treatment groups in mean FEV₁ change from baseline after 48 weeks. The p-value for the null hypothesis of no difference and a two-sided 95% confidence interval for the difference will be provided. The comparison between treatment groups at all the other visits (2-8) will also be presented.

A figure of observed mean change from baseline and standard errors at each visit, by treatment group will be presented. A figure with adjusted mean changes from baseline at each visit by treatment group derived from the LMM will be provided.

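### SAP 9.4 lets an unscheduled spirometry session replace the scheduled one and, as most naturally read, gives a patient two rows in a visit window, while the by-visit tests need one

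*SAP*

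**What the plan says.** - **Allocation (SAP 9.4).** "Measurements (both scheduled and unscheduled) will be allocated to visits (and analyzed") by Table 1, after rejected spirometry has been removed.
- **Choice within a window (SAP 9.4).** With two or more values, "only the one closest to the scheduled time of the visit will be used in the analysis, unless an additional measurement will be the last" one of the patient's participation. That last value is always kept; the example given is an unscheduled visit before early withdrawal. The scheduled session is preferred outright only when both sessions share a date.
- **Day count (SAP 9.4, Table 1).** Windows use visit date minus randomization date, with no +1. V9 covers days 309-364 for patients not entering the extension and 309-385 for those who do. V10 covers 365-385.
- **Unscheduled visits (Protocol 14.2.7).** "Whenever medically warranted, the Investigator may ask the patient to appear or the patient may elect to appear at the clinic for an unscheduled visit".
- **Permitted deviations (Protocol, Schedule of Activities).** ±7 days for V2-V5 and V10, ±14 days for V6-V9.
- **By-visit tests.** SAP 14.2.2: "A two-sample t-test will be performed by treatment group at each visit using change from baseline in" FEV₁. SAP 14.2.1 adds an ANCOVA at Week 48, and SAP 14.5 adds subgroup t-tests.
- **Primary model.** SAP 14.1.3: "The primary efficacy analysis will be carried out using a LMM for repeated measurements, using all observed available" FEV₁ values. SAP 14.1.5 places them at their actual visit times.

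**The concern.** The rule raises two separate problems.

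The first is displacement. Scheduled visits may lie one or two weeks off the nominal day, so an unscheduled session can be nearer and win. Some unscheduled sessions are prompted by a clinical problem, so the value carried as Week 48 in a by-visit table may not come from the planned visit.

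The second is the last-measurement exception. If both values stay, one patient supplies two rows to a test that treats rows as independent patients. The reported standard error is then too small, and the patient concerned gets double weight. If the last value instead overrides the closest, a late value before withdrawal takes the place of the better-timed one. Two programmers could reasonably implement these differently.

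It is also unclear whether the windowed values or all values feed the primary model, and that choice determines how far either problem reaches.

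**Working it through.** **1. The plan's own figure.** SAP 8.2 uses "an independent samples t-test with a one-sided type I error level of" 0.025, a difference of "200 mL (0.2 L) and a standard deviation of 350 mL (0.35 L"), and at least 80% power when "the sample size in each treatment group is at least 50 patients".
- Normal approximation: n = 2 × (1.960 + 0.842)² × (350/200)² = 48.1, so 49 per arm.
- The t-test needs 49.05, so 50; power at 50 per arm is 80.8%. The figure reproduces.
- The Protocol synopsis allows about 10% drop-out: 50/0.9 = 55.6, so 56 per arm or 112 in total, close to the stated 110.

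The SD of 350 mL therefore serves as yardstick. SAP 8.2 reports 62 randomized. With an equal split and one value each, n = 31 per arm and SE = 350 × √(2/31) = 88.9 mL.

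**2. Displacement at V9.** On the window formula Week 48 is day 336. Assume the scheduled session is uniform over days 322-350 (29 days) and one unscheduled session is uniform over the SAP window, with same-date pairs excluded. If the scheduled session is d days off, the unscheduled one is nearer on 2d − 1 days. Summed over d = 1 to 14 on both sides, this is 2 × 14² = 392 pairs.
- Window 309-364 (56 days): 392/(29 × 55) = 392/1,595 = 24.6%.
- Window 309-385 (77 days): 392/(29 × 76) = 392/2,204 = 17.8%.
- The same count at V2-V8 gives 15.9% to 24.6%.

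These are shares of the windows that already hold an eligible unscheduled session. A scheduled session exactly on the nominal day cannot be displaced.

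Effect on a mean: one value 300 mL lower (assumed) moves an arm mean by 300/31 = 9.7 mL, or 9.7/88.9 = 0.11 SE. If 1 to 5 values in one arm only are 100 to 200 mL lower (assumed), the shift runs from 100/31 = 3.2 mL to 5 × 200/31 = 32.3 mL.

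**3. Two rows per patient.** Let k patients per arm give two rows with within-patient correlation ρ. The variance of the arm mean is inflated by 1 + 2kρ/(n + k). The t-test reports SE = 350 × √(2/(n + k)); the true SE is that times the square root of the inflation. The real error is 2 × [1 − Φ(1.96/√inflation)]. With n = 31, and k and ρ assumed:

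| k | ρ | Inflation | SE reported (mL) | True SE (mL) | Real two-sided error |
|---|---|---|---|---|---|
| 1 | 0.7 | 1.044 | 87.5 | 89.4 | 5.5% |
| 3 | 0.7 | 1.124 | 84.9 | 90.0 | 6.4% |
| 3 | 0.9 | 1.159 | 84.9 | 91.4 | 6.9% |
| 5 | 0.9 | 1.250 | 82.5 | 92.2 | 8.0% |

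With 25 per arm the range is 5.6% to 8.6%.

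Double weight also shifts the mean. If the k patients are in one arm only and are D mL worse than the rest, the shift is 2kD/(n + k) − kD/n. For k = 1, D = 200: 12.5 − 6.5 = 6.0 mL. For k = 5, D = 400: 111.1 − 64.5 = 46.6 mL. The one-sided occurrence and D are assumptions.

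**4. A route that needs neither illness nor withdrawal.** Week 52 is 52 × 7 = day 364 on the window formula, which lies inside the 309-364 V9 window. V10 is permitted on days 357-371, and 8 of those 15 days (357-364) fall in V9. Such a V10 value, being the last, would be kept beside the true V9 value. This concerns only patients not entering the extension. It touches the on-site analysis only if V10 uses the on-site spirometer, and the device is redacted.

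**5. What feeds the primary model.** SAP 9.4 introduces windows for by-visit presentation, then speaks of analysis in general and of one value per window. SAP 9.5.1 and 14.1.3 call for all observed data, and SAP 14.1.5 uses actual times. The second group points to all values; the SAP never says so outright.

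**The case against.** The strongest reply is that the primary analysis is probably untouched. If the mixed model takes all accepted values at their actual days, nothing is displaced and an extra value is an ordinary repeated measure. That stands, and it limits the point mainly to by-visit summaries and to tests the SAP itself calls supplementary and descriptive.

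Three stronger inferences are tempting, and the documents do not support them.
- **That sick visits systematically replace planned ones.** Protocol 14.2.7 also lets patients choose to come. Extra sessions may confirm progression at least two weeks later, or repeat a rejected test. Study spirometry is not required at every unscheduled visit, and SAP 14.1.1 admits only accepted on-site values.
- **That patients certainly count twice.** This is the more natural reading of the exception, but replacement of the closest value by the last is also possible.
- **That unscheduled visits differ by arm.** The trial is open-label, so they could, but no figure in the documents shows it.

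It can also be said that the closest-value rule is prespecified and the same in both arms, and that an accepted value is not invalid because it was unscheduled. That is fair for displacement, which is partly a matter of preference. It does not answer the double rows, where the t-test's independence assumption fails under a stated rule.

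**Conclusion.** The point holds as a defect in the window rule with modest reach. Displacement follows from the text whenever an accepted unscheduled session is nearer the nominal day. The last-measurement exception either breaks the one-row-per-patient requirement of SAP 14.2.1, 14.2.2 and 14.5 or silently overrides the closest value, and the SAP does not say which.

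The error range of about 5.5% to 8% rests on assumed counts and correlations, and the shift of about 10 mL per displaced value rests on an assumed 300 mL drop. How often eligible unscheduled sessions occur is not stated, so the overall effect cannot be estimated. Subgroup t-tests are more exposed, since SAP 14.5 aims at only 10 or more patients per stratum and one extra row weighs more there.

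A reader might infer that the primary Week 48 estimate is biased. The documents do not support that. What they leave open is which dataset the model uses, and that should be settled in writing. The descriptive status lowers the stakes, but tests and intervals are still to be reported.

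**What to change.** Amend SAP 9.4 and align 14.1.3:

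1. State that each patient contributes one value per nominal visit to all by-visit t-tests (including subgroup tests), the ANCOVA and summaries.
2. Within a window, use the accepted session of that nominal scheduled visit; use an unscheduled session only if there is none.
3. Let extra and last measurements enter the mixed model only, at their actual day, and state that the model uses all accepted values.
4. Align the V9/V10 boundary with the day count. V9 is permitted up to day 336 + 14 = 350 and V10 from day 364 − 7 = 357, so ending the V9 window anywhere from 350 to 356 separates the two for patients not entering the extension.

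The cost is SAP wording and matching dataset specifications, with no new data. The downside is that a scheduled value slightly further from the nominal day will sometimes be used in place of a nearer unscheduled one.
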